### *Hypothesis:*

The working hypothesis is that MR imaging 2 to 3 weeks after surgery is no worse in quality and utility than immediately postoperatively (within 72 hours).

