### *Primary aim:*

Assess if Magnetic Resonance Imaging (MRI) at 2 to 3 weeks after surgery (aka: later imaging) leads to the same clinical decisions and has the same probability of being chosen by a physician for guiding the subsequent management of the patient, compared with immediately postoperative MRI (within 72 hours, aka: early imaging).

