### *Sample:*

Patients admitted to Cleveland Clinic for surgical management of metastatic extradural spinal tumors will be considered for the study. We anticipate the initial enrollment of 8 patients, which is a number chosen arbitrary for the pilot study. Based on results of this study we will perform power analysis and determine the number of subjects needed to get statistically significant results. Inclusion will not depend in any way on age, gender, ethnicity, or any other personal characteristics other than clinical relevance. We expect the study population to be similar to the spine surgery population seen at the Cleveland Clinic for neoplastic pathologies.

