### **5.0 RESEARCH PLAN**

#### *Imaging protocol:*

We will identify the patients meeting the above criteria and consent them for the study. Another MRI will be obtained 2-3 weeks postoperatively. The routine spine MRI protocol will be utilized, which includes the following sequences: haste localizer, sagittal T1, T2, and STIR, axial T2 for lumbar spine or axial gradient echo for cervical and thoracic spine, axial T1, post contrast sagittal and axial T1. All scans will be obtained using a 1.5 Tesla magnet. When indicated, sedation or anxiolysis and IV hydration for low glomerular filtration rate will be administered by radiology per protocol.

*Image analysis:*

The image acquisition dates will be blinded and the images independently reviewed by two neuroradiologists, a radiation oncologist, and a spine surgeon. Each of them will compare and choose a better-quality image. These results will be compared and inter-observer variability will be established.

Radiology (2 independent neuro-radiologists) will be blinded to all quantitative data (including the date of post-op MRI) and they will be asked to evaluate the following parameters:

- a. Level(s) of surgery = number ie L3, L4
- b. Presence of hardware = Y or N
- c. Does hardware obscure canal = Y or N
- d. Nature of surgery = 0 separation surgery/decompression only, 1 corpectomy, 2 combination of 0+1
- e. Fluid collection = AP\*Lateral\*CC in CM
- f. Epidural disease pre op = SOSG grading system AND max thickness at N level
- g. Epidural disease post op = SOSG grading system AND max thickness at N level
- h. Nature of marrow replacement (preop and residual on post op) = 1-4 for 25%, 50%, 75%, and 100% replaced respectively
- i. Compression fracture pre and post = Y or N
- j. Adjacent level involvement pre and post = Y or N

Spine surgeon and radiation oncologist will be blinded to date and use a scale of

- a. 0 = not confident,
- b. 1 = confident
- c. 2 = very confident

in terms of confidence in contouring/tumor targeting using a particular image set

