## **8.0 STATISTICAL CONSIDERATIONS**

Power analysis was not performed for this pilot study, since magnitude of differences is unknown. Obtained data will be used for designing a larger study. Kappa statistics will be calculated to evaluate the inter-rater reliability for the primary aim. For the secondary aims, descriptive statistics will be used.

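### The four-reader image-quality comparison has no 'equal' answer, so scans that look equally good are recorded as arbitrary preferences, which fits poorly with a 'no worse' hypothesis

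*Combined protocol and SAP*

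**What the plan says.** Section 5.0, Image analysis, has the images "independently reviewed by two neuroradiologists, a radiation oncologist, and a spine surgeon", with acquisition dates masked. The comparison itself is one sentence: "Each of them will compare and choose a better-quality image". The choices are then used as follows: "These results will be compared and inter-observer variability will be established". No tie or no-preference answer is described, and none is expressly ruled out. The reading form is not in the document.

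The same section gives the spine surgeon and the radiation oncologist a 0/1/2 confidence scale for contouring and targeting on a given image set. The two neuroradiologists record findings (fluid collection, epidural grade and thickness, marrow replacement and others) but no quality score.

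The hypothesis in section 1.0 is that "MR imaging 2 to 3 weeks after surgery is no worse in quality and utility than immediately postoperatively (within 72 hours"). The primary aim in section 2.0 asks whether later MRI "leads to the same clinical decisions and has the same probability of being chosen by a physician".

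Section 8.0 gives one analysis for the primary aim: "Kappa statistics will be calculated to evaluate the inter-rater reliability for the primary aim". It states no margin, no power calculation and no estimate of how often each scan is chosen. Section 2.0 (Sample) sets the size: "We anticipate the initial enrollment of 8 patients, which is a number chosen arbitrary for the pilot study". Both sections say the results will be used to plan further work.

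**The concern.** If later MRI is no worse because the two scans are about equally good, the typical reader looking at a typical patient has no real preference. The task as described still asks for a winner. The recorded answer is then a guess or a habit, and nothing in the data marks it as one. A vote for the early scan that means 'no difference' cannot be separated from one that means 'the later scan is worse'. Two readers who both regard the scans as equal can be recorded as disagreeing.

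Two things are at stake. First, the planned primary statistic measures agreement between readers, and agreement on arbitrary votes is expected at chance level. Equal scans would then look like unreliable reading. Second, the pilot is meant to inform a larger study. The share of tied pairs is a basic planning input for a paired preference comparison, and it cannot be recovered later without re-reading the scans.

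**Working it through.** The documents give no power, margin or derived sample size, so there is no stated figure to reproduce. The check asks what the described task yields when scans are equal.

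**Inputs from the documents.** 8 patients (section 2.0, Sample); 4 independent readers, one choice each per patient (section 5.0); kappa as the primary-aim statistic (section 8.0).

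**Assumptions, not in the documents.** Readers act independently and choose 50:50 when scans are equal. Where an 'equal' answer exists, they use it correctly 80% or 90% of the time. Kappa results are for Fleiss kappa over 100,000 simulated pilots per scenario.

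**1. All 8 pairs equal, two-way choice.**
- Agreement of any two readers: 0.5² + 0.5² = 50%.
- All four readers agree on a patient: 2 × 0.5⁴ = 12.5%.
- Mean kappa -0.03; 95% of pilots between -0.25 and 0.29; kappa at or below 0.20 in 93%.
- One reader splits 6:2 or wider: 2 × (28 + 8 + 1)/256 = 74/256 = 28.9%.
- At least one of four readers does so: 1 - (1 - 0.289)⁴ = 74%.
- One reader splits exactly 4:4: 70/256 = 27%. The exact 95% interval for 4/8 is 16% to 84%.

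**2. Some pairs equal, later scan better in the rest (and always so read).** Expected share of patients in whom early is named better = 0.5 × tied share, although early is better in none:
- 50% tied: 0.5 × 0.50 = 25%
- 75% tied: 0.5 × 0.75 = 38%
- 100% tied: 0.5 × 1.00 = 50%

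**3. Does an 'equal' answer help?**

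| Scenario | Answers allowed | Pairwise agreement | Mean kappa |
|---|---|---|---|
| All 8 equal | two | 50% | -0.03 |
| All 8 equal, 80% correct use | three | 0.8² + 2 × 0.1² = 66% | -0.03 |
| All 8 equal, 90% correct use | three | 0.9² + 2 × 0.05² = 82% | -0.03 |
| 6 equal, 1 early better, 1 later better | two | 59% | 0.16 |
| Same, 90% correct reading | three | 82% | 0.62 |

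With all pairs equal, four-reader unanimity rises from 12.5% to 41% (80% correct use) or 66% (90%). Kappa does not move, because almost all readings fall in one category. It is undefined if every reading is 'equal'.

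**4. Counter-check.** Suppose 4 patients truly favour early and 4 truly favour later, with 90% correct reading and a two-way choice. The later share again averages 50%, but mean kappa is 0.64. Kappa therefore helps to separate equal scans from patient-level preferences that cancel. It does not separate equal scans from readers who hold real but conflicting views of the same patients, since both can put kappa near chance.

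**The case against.** A reader might infer that equality cannot be recorded at all. The documents do not support that. The primary aim asks partly whether later MRI "has the same probability of being chosen by a physician for guiding the subsequent management of the patient", which is itself a statement about choices; under equality a two-way choice has an expected later share of 50%. The surgeon and radiation oncologist can give both scans the same confidence score, and that score bears on the utility half of the hypothesis. The neuroradiologists can record identical findings on both scans. These points stand and confine the gap to the overall quality choice for an individual patient.

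A reader might also infer that equal scans would make a true 100% 'no worse' rate appear as 50%. That requires defining 'no worse' as equal or late better, which the documents never do, and scoring every early vote against the later scan, which they do not plan. The shares in step 2 are illustrations under assumed tie rates. It would likewise go too far to say that the problem persists whatever statistic is used (step 4), or that this pilot alone decides when MRI is done; the plan assigns it no such role.

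Two further points have force. The absence of a tie answer is inferred from silence in a one-sentence description. Forced choice is also a legitimate design, because it stops readers retreating to 'equal'. But the sentence reads naturally as picking one scan, and section 5.0 spells out response codes for most other reader items. The mitigations are also partial: section 8.0 plans no estimate of the later share, 4/8 is compatible with 16% to 84%, and the confidence scale concerns contouring and is not given to the neuroradiologists. A follow-up lean question keeps the forced-choice data, which answers the design objection.

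**Conclusion.** The point holds in a limited form. As described, the patient-level quality choice cannot distinguish no preference from a real preference, and this falls mainly on the neuroradiologists. If the scans are equal, kappa is expected near 0 (mean -0.03, at or below 0.20 in 93% of simulated pilots), and the tied share is lost. Where most but not all pairs are equal, the response format alone moves mean kappa from 0.16 to 0.62 and agreement from 59% to 82%. These figures rest on independent readers, 50:50 guessing on ties and the stated accuracy of reading; habit-driven or correlated choices would change them. The change is worth making before reading starts, but its absence does not invalidate the pilot. If the reading form already allows ties, a sentence saying so settles the collection part.

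**What to change.** **Section 5.0.** For each reader and patient, record 'Scan A better', 'equal' or 'Scan B better', once for image quality and once for the scan the reader would use to guide management. When 'equal' is chosen, ask for a forced lean so that the two-way choice is kept.

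**Section 8.0.** After unmasking, report the proportions early better, equal and late better. Define 'late no worse' as (equal + late better)/n, and give a confidence interval that allows for several readers per patient. Report raw agreement beside kappa, because kappa is near 0 or undefined if nearly all readings are 'equal'.

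**Cost.** A few extra boxes on the reading form; no extra scans, patients or readers. The downside is that readers may overuse 'equal', leaving fewer decided pairs. The lean question limits this.

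### The primary aim has no designated early-versus-late estimate: four readers' image choices and two readers' confidence scores are collected, but only an inter-rater kappa is assigned to the aim

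*Combined protocol and SAP*

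**What the plan says.** - **Hypothesis (Section 1.0).** Late imaging is "no worse in quality and utility than immediately postoperatively (within 72 hours". Two properties are claimed: quality and utility.
- **Primary aim (Section 2.0).** Whether late imaging "leads to the same clinical decisions and has the same probability of being chosen by a physician" as early imaging, the choice being the scan used to guide later management.
- **Image analysis (Section 5.0).** Four date-blinded readers: two neuroradiologists, one radiation oncologist and one spine surgeon. "Each of them will compare and choose a better-quality image". The results are then to be compared and inter-observer variability established. The spine surgeon and the radiation oncologist also give a 0-2 score "in terms of confidence in contouring/tumor targeting using a particular image set".
- **Statistical considerations (Section 8.0).** Kappa for inter-rater reliability is the only statistic given for the primary aim; the secondary aims get descriptive statistics. "Power analysis was not performed for this pilot study, since magnitude of differences is unknown". The data are to be used to design a larger study.
- **Sample (Section 2.0).** "We anticipate the initial enrollment of 8 patients, which is a number chosen arbitrary for the pilot study". A power analysis for the next study is to be based on the results.

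**The concern.** The aim is a comparison of early with late. The assigned statistic measures agreement between readers, which is a different quantity. Followed as written, the plan yields no designated estimate of how often the late scan is chosen.

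The data allow six early-versus-late contrasts: four choices and two confidence scores. The documents do not say which reader is the physician of the aim, how four choices per patient become one result (2-2 ties are possible), or which measure counts if choice and confidence point in different directions. The confidence score is the recorded item closest to the hypothesised utility. It is not among the secondary aims, and neither Section 2.0 nor Section 8.0 explicitly assigns it to an aim or gives it an early-versus-late comparison.

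At stake is the pilot's main product. A planning proportion for the larger study needs a defined reader and a defined measure. Without them, the figure carried forward can be selected after the data are seen.

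**Working it through.** The plan states no power, alpha, margin or effect size, so it has no figure to reproduce. The checks below are illustrations under stated assumptions.

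**Inputs from the documents.** 8 patients (Section 2.0, Sample); 4 readers each making a binary choice, 2 of whom also give a 0-2 score (Section 5.0); kappa for the primary aim (Section 8.0).

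**Assumptions made here.** No true preference (p = 0.5). A split of 7/8 or stronger in either direction serves as an illustrative lopsided result. Readers' choices come from normal variables correlated within patient, with the correlation varied from 0 to 0.9 because the documents give none.

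**1. Kappa does not answer the aim.** If all four readers agree on every patient, Fleiss kappa is 1.0 whether the late scan is chosen in 7/8, 4/8 or 1/8 of patients. The same kappa fits opposite answers.

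**2. Room for selection after the fact.**
- One named reader: P(7 or more of 8, either way) = 2 × (8 + 1)/256 = 18/256 = 0.070.
- Any of four independent readers: 1 − (1 − 0.0703)^4 = 0.253.
- Any of four correlated readers (simulation, 200,000 runs):

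| Correlation | 0 | 0.3 | 0.5 | 0.7 | 0.9 |
|---|---|---|---|---|---|
| At least one reader at 7/8 or stronger | 0.25 | 0.25 | 0.23 | 0.21 | 0.16 |

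This is 2.3 (0.162/0.0703) to 3.6 (0.253/0.0703) times the single-reader figure. The two confidence contrasts are not included.

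**3. What a four-reader average would hide, and what kappa would show.** Suppose both neuroradiologists choose early in 8/8 and the other two readers choose late in 8/8. The pooled proportion is (0 + 0 + 8 + 8)/32 = 50%. Every patient is split 2-2, so observed pairwise agreement is (2² + 2² − 4)/(4 × 3) = 1/3, and chance agreement is 0.5² + 0.5² = 0.5. Fleiss kappa = (1/3 − 1/2)/(1 − 1/2) = −0.33. The planned kappa exposes the disagreement but does not say whose choice answers the aim.

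**4. How often readers would truly oppose each other.** With no true preference, at least one reader at 5/8 or more late and another at 3/8 or less occurs in 68%, 44% and 16% of pilots at correlations 0, 0.5 and 0.9. The exact 95% intervals for these results (5/8: 24% to 91%; 3/8: 9% to 76%) overlap widely. At the 7/8 cut-off used in step 2, opposing results occur in about 1.4%, 0.2% and 0%.

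**5. Precision once one reader is named.** Exact 95% intervals at n = 8: 4/8 gives 16% to 84%; 7/8 gives 47% to 99.7%; 8/8 gives 63% to 100%.

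**The case against.** The strongest reply is that this is an arbitrary-size pilot with no alpha, test or success rule, so choosing a reader afterwards crosses no threshold. Showing all four readers side by side would be a reasonable way to explore reader variability. This stands as a limit on severity: there is no confirmatory conclusion to get wrong. It does not remove the point. The output is meant to feed a power analysis, and an estimate for that purpose has to be defined.

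Three stronger readings are tempting but not supported:

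- **That opposing disciplines will average to a false finding of equal probability.** No section plans to average the choices, and kappa would be −0.33 in the extreme case (step 3).
- **That the same 8 patients would often support opposite conclusions.** The 44% in step 4 depends on the loose 5/8 versus 3/8 cut-off; at 7/8 it is about 0.2% at correlation 0.5.
- **That the confidence score belongs to no aim.** Confidence in contouring can fairly be read as part of guiding management, and the primary-aim kappa could then cover it. The text is silent on the mapping, and even on that reading kappa gives no early-versus-late comparison of the score.

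Two further cautions bear on any remedy. Averaging two readers can cancel just as pooling four can. And the primary aim says only that a physician chooses, so restricting the estimate to two readers is a judgement, resting on the fact that Section 5.0 puts the contouring question to those two alone.

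**Conclusion.** The concern holds as an omission in the estimate. The aim asks how often the late scan is chosen to guide management; the plan assigns it only a reliability statistic, designates none of the six available contrasts, and gives the contouring-confidence score no stated comparison. The consequence is an ambiguous pilot estimate carried into the larger study's design, with some room for selection after the fact: 0.07 for one named reader against 0.16 to 0.25 for any of four. Those figures assume no true preference, a 7/8 cut-off chosen here, and a between-reader correlation from 0 to 0.9. The single-reader figure is exact; the correlated ones depend on the assumed model. The change should be made, but this is not a flaw that makes the pilot unusable.

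**What to change.** In Sections 2.0 and 8.0:

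- **Primary estimate.** Name the proportion of patients for whom the late scan is chosen, reported separately for the radiation oncologist and the spine surgeon, each with an exact 95% interval at n = 8.
- **Single summary, if wanted.** Use the within-patient average of these two readers, always shown with both readers' own results and the number of patients on whom they disagree.
- **Key supporting measure of utility.** Name the paired late-minus-early confidence score of the same two readers.
- **Neuroradiologists.** Report their choices separately and do not pool them into the primary estimate.
- **Other statistics.** Keep kappa as supportive and label the remaining contrasts exploratory.

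The cost is a few sentences, with no extra scans, readers or patients. The primary estimate rests on two readers instead of four, so it is slightly less precise, and the intervals stay wide (4/8 gives 16% to 84%).

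Two gaps remain. The recorded item asks for the better-quality image, whereas the aim concerns the scan chosen to guide management. The part of the aim about reaching the same clinical decisions has no recorded variable. The report should say so when it presents the estimate.

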### *Secondary aims:*

Investigate the differences between early and late MRI by comparing:

Size of tumor in three dimensions;

Extent of edema;

Presence and extent of fluid collection;

Spine Oncology Study Group score;

Involvement of adjacent levels;

Progression of tumor;

Patient's preference/performance scale right after each image had taken: level of discomfort (measured by visual analog scale) at around the time (within 48 hours) each MRI was performed.

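### Adjacent-level involvement is read only as Y or N, so two positive post-operative scans show no early-late difference even when they show different or additional levels

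*Combined protocol and SAP*

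**What the plan says.** The secondary aims (section 2.0) are introduced with "Investigate the differences between early and late MRI by comparing", and one of the seven listed items is "Involvement of adjacent levels". Another is "Progression of tumor".

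The reading list for the two neuroradiologists (section 5.0, Image analysis, items a to j) serves the adjacent-level aim through item j alone: "Adjacent level involvement pre and post = Y or N". Other items do use vertebral levels, but for other purposes. Item a names the operated segment, "Level(s) of surgery = number ie L3, L4". Items f and g tie a thickness to a level for epidural disease; item g, for example, reads "Epidural disease post op = SOSG grading system AND max thickness at N level". Item h grades marrow replacement from 1 to 4 without tying the grade to an adjacent level.

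There are three scans (section 6.0): pre-operative, 72 hours after surgery, and a later one, of which section 5.0 says "Another MRI will be obtained 2-3 weeks postoperatively". Item j refers to the post-operative state once and does not separate the two post-operative scans.

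On analysis, section 8.0 says "For the secondary aims, descriptive statistics will be used". The planned enrolment is 8 patients, a number described as arbitrary, and the data are meant to inform a larger study.

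**The concern.** The aim asks whether the early and late scans differ in adjacent-level involvement. A single Y/N per scan can show that one scan is positive and the other is not. It cannot show that both are positive in different places, or that one shows an extra level. If the early scan shows the level above the operated segment and the late scan the level below, item j gives Y and Y.

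What is at stake is the descriptive result for this aim and its use in designing the larger study. Tumor progression is affected to a lesser degree. It has no item of its own on the reading list, and a newly involved level is one reading from which it might be derived. Y/N cannot show a new level in a patient who is already Y. The loss happens when the form is filled in, so no choice of summary statistic recovers it; the scans would have to be read again.

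**Working it through.** The plan has no figure to reproduce: no power analysis was done, and no rate of adjacent-level involvement is given. The check is therefore an enumeration of what item j can and cannot show.

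**Inputs.** From the documents: item j is binary; the comparison is early versus late; item j is taken as completed for each post-operative scan, since the aim requires it. Assumed for illustration only: there are two possible adjacent levels, one above (A) and one below (B).

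**Step 1: all early/late pairs.** Each scan has 4 possible states: none, A, B, or A and B. That gives 4 × 4 = 16 pairs. In 4 pairs the states are identical, so 16 − 4 = 12 truly differ. Item j shows a difference only when one scan is none and the other is one of the 3 positive states: 1 × 3 + 3 × 1 = 6. So Y/N shows 6 of the 12, and 12 − 6 = 6 are hidden. Recording by level would show all 12.

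**Step 2: both post-operative scans positive.** There are 3 × 3 = 9 such pairs. In 3 the level sets are identical, so 9 − 3 = 6 differ. All 6 are coded Y/Y, and item j shows 0 of 6.

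**Step 3: positive before surgery.** With the pre-operative reading fixed at Y there are 2 × 2 = 4 early/late patterns: Y-Y, Y-N, N-Y and N-N. Two of these, Y-N and N-Y, do show an early-late difference, so a positive pre-operative reading does not by itself remove the contrast. Now suppose level A was positive before surgery and is still seen on both later scans. Each later scan is then A alone, or A and B, giving 2 × 2 = 4 pairs. Two of these differ (a further level on one scan only), and item j shows 0 of 2.

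**Step 4: direction.** If the two level lists are identical, their Y/N codes are identical too. Collapsing can therefore hide a difference but never produce one.

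These are counts of patterns, not frequencies. The patterns are not equally likely, and nothing in the documents says how likely each is.

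**The case against.** The strongest reply is that this is a coarse scale on one of seven descriptive secondary items in an 8-patient pilot. No test, margin or concordance rule depends on item j. Part of any difference may also appear elsewhere: items f and g would pick up epidural disease at a level, all four readers compare the images directly, and the surgeon and radiation oncologist rate their confidence in contouring on each image set. This stands as a limit on the consequence. It does not remove the gap, because items f and g cover epidural disease only and none of the other readings records which adjacent level is involved.

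Three stronger readings are tempting, and the documents do not support them.

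- A reader might infer that every patient positive before surgery is uninformative, and turn an assumed prevalence into a number of lost patients. Step 3 shows that such a patient can still be read Y on one post-operative scan and N on the other. The plan's own background says early images may be of poorer quality and confounded by surgical change, which makes that plausible. No prevalence is given.
- A reader might infer a bias towards the answer the trial hopes for. The hypothesis concerns image quality and utility, and the primary aim concerns clinical decisions and the physician's choice of scan. Item j feeds neither, and the secondary aims are framed as a search for differences.
- A reader might infer that item j conceals a disagreement that would change the radiation target. Nothing in the plan says targeting is derived from this item.

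**Conclusion.** The concern holds in a limited form. A patient read Y on both post-operative scans, including one positive before surgery whose involvement is still seen on both, shows no early-late difference on this aim even if the scans show different or additional levels. The loss runs one way, towards apparent agreement on this item.

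Its size cannot be estimated from the documents. The pattern counts (6 of 12 differing pairs hidden overall, and 6 of 6 where both scans are positive) rest on the two-level illustration and are not probabilities. One patient is 1/8 = 12.5 percentage points of any proportion here, but that is true of every binary item in the pilot and does not measure harm. The primary aim and the sample size are unaffected. The change is worth making because it costs little, and because named levels can be collapsed to Y/N later, whereas Y/N cannot be expanded without re-reading.

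**What to change.** Change item j so that each neuroradiologist lists the involved adjacent levels by name, or none, separately for the pre-operative, early and late scans, in the style item a already uses for the operated levels. This also removes the ambiguity over which post-operative scan the item refers to.

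Add one sentence to section 8.0: early-late agreement on adjacent levels is described within each reader, by comparing that reader's early list with the same reader's late list, and any level that is new relative to the pre-operative scan is reported separately. Comparing within reader keeps differences between the two neuroradiologists from being counted as differences between the scans.

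The cost is one changed line on the reading form and slightly more form entry. No extra scan or patient is needed.
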